#### Example of valid data

#### Example of invalid data

11. Log the non-wear times (6 hours of consecutive sitting or standing) here: Z:\[name] Lab\Stand and Move ASU\_UMN\Data\ActivPAL\Errors.xlsx

12. To save the PAL file as a PDF, click the 'print' icon on the upper left corner of the activPAL screen. Click OK

13. A screen will prompt you to save the file à Save the file on (X:\Research\[name] Lab\Stand and Move ASU\_UMN\Data\Participant Feedback\T#\ID#\_T#).

14. The file should now be saved in the corresponding folder as a PDF.

- The PDF file can be sent to participants as feedback either by email or by printing.
- Refer to Sending activPal Feedback Protocol to email

**Appendix 1.4. activPAL processing SAS code.**

\*\*\*\*\*/

\*ActivPAL Processing:

\* Outputs the following variables:

- \* 1. Long\_sitbouts\_dur - Total mins spent sitting > 30 mins bouts
- \* 2. Long\_sitbout\_ct - Number of long sitting bouts
- \* 3. Short\_sitbout\_dur - Total mins spent sitting < 30 mins bouts
- \* 4. Short\_sitbout\_ct - Number of short sitting bouts
- \* 5. Sit - Total minutes spent sitting
- \* 6. Stand - Total minutes spent standing
- \* 7. LPA - Total minutes spent on LPA (stepping activities with cadence <100 steps/mins) \*
- \* 8. MVPA - Total minutes spent on MVPA(stepping activities with cadence <100 steps/mins) \*

\*\*\*\*\*/

/\*\*\*\*\*\*/

/\*Set libref \*/

## SMW Study Manual of Procedures

---

/\*\*\*\*\*/

```
LIBNAME SMASU 'P:\Sample_SMASU\';  
Libname Track "X:\[name] Lab\Stand and Move  
ASU_UMN\Data\ActivPAL\ISO_TEST\SAS_FILES\DailyLogs";
```

```
LIBNAME ISO 'X:\[name] Lab\Stand and Move  
ASU_UMN\Data\ActivPAL\ISO_TEST\SAS_FILES\DATASETS';
```

\*Create temnplate for daily summary;

```
DATA iso.Report_Final;  
  INPUT  
    ID  
    Mtime  
    Date  
    P1_Sitstand  
    P1_long_sitbout_ct  
    P1_long_sitbout_dur  
    P1_short_sitbout_ct  
    P1_short_sitbout_dur  
    P1_min  
    P1_Sit  
    P1_Stand  
    P1_LPA  
    P1_MVPA  
    P1_Step_min  
    P1_Step_ct  
    P1_step00_05  
    P1_step05_10  
    P1_step10_15  
    P1_step15_30  
    P1_step30_60  
    P1_step60_90  
    P1_step90_120  
    P1_step120_up  
    P1_nbouts_sed  
    P1_alphasit  
    P1_parm1_sit  
    P1_x50_sit  
    P1_min_t_sit  
    P1_max_t_sit  
    P1_totsed
```

P1\_nbouts\_sed\_tot  
P1\_ginisit  
P1\_mean\_period  
P2\_Sitstand  
P2\_long\_sitbout\_ct  
P2\_long\_sitbout\_dur  
P2\_short\_sitbout\_ct  
P2\_short\_sitbout\_dur  
P2\_min  
P2\_Sit  
P2\_Stand  
P2\_LPA  
P2\_MVPA  
P2\_Step\_min  
P2\_Step\_ct  
P2\_step00\_05  
P2\_step05\_10  
P2\_step10\_15  
P2\_step15\_30  
P2\_step30\_60  
P2\_step60\_90  
P2\_step90\_120  
P2\_step120\_up  
P2\_nbouts\_sed  
P2\_alphasit  
P2\_parm1\_sit  
P2\_x50\_sit  
P2\_min\_t\_sit  
P2\_max\_t\_sit  
P2\_totsed  
P2\_nbouts\_sed\_tot  
P2\_ginisit  
P2\_mean\_period  
P3\_min  
P3\_Sitstand  
P3\_long\_sitbout\_ct  
P3\_long\_sitbout\_dur  
P3\_short\_sitbout\_ct  
P3\_short\_sitbout\_dur  
P3\_Sit  
P3\_Stand  
P3\_LPA  
P3\_MVPA  
P3\_Step\_min

P3\_Step\_ct  
P3\_step00\_05  
P3\_step05\_10  
P3\_step10\_15  
P3\_step15\_30  
P3\_step30\_60  
P3\_step60\_90  
P3\_step90\_120  
P3\_step120\_up  
P3\_nbouts\_sed  
P3\_alphasit  
P3\_parm1\_sit  
P3\_x50\_sit  
P3\_min\_t\_sit  
P3\_max\_t\_sit  
P3\_totsed  
P3\_nbouts\_sed\_tot  
P3\_ginisit  
P3\_mean\_period  
P4\_Sitstand  
P4\_long\_sitbout\_ct  
P4\_long\_sitbout\_dur  
P4\_short\_sitbout\_ct  
P4\_short\_sitbout\_dur  
P4\_min  
P4\_Sit  
P4\_Stand  
P4\_LPA  
P4\_MVPA  
P4\_Step\_min  
P4\_Step\_ct  
P4\_step00\_05  
P4\_step05\_10  
P4\_step10\_15  
P4\_step15\_30  
P4\_step30\_60  
P4\_step60\_90  
P4\_step90\_120  
P4\_step120\_up  
P4\_nbouts\_sed  
P4\_alphasit  
P4\_parm1\_sit  
P4\_x50\_sit  
P4\_min\_t\_sit

## SMW Study Manual of Procedures

---

P4\_max\_t\_sit  
P4\_totsed  
P4\_nbouts\_sed\_tot  
P4\_ginisit  
P4\_mean\_period  
P5\_Sitstand  
P5\_long\_sitbout\_ct  
P5\_long\_sitbout\_dur  
P5\_short\_sitbout\_ct  
P5\_short\_sitbout\_dur  
P5\_min  
P5\_Sit  
P5\_Stand  
P5\_LPA  
P5\_MVPA  
P5\_Step\_min  
P5\_Step\_ct  
P5\_step00\_05  
P5\_step05\_10  
P5\_step10\_15  
P5\_step15\_30  
P5\_step30\_60  
P5\_step60\_90  
P5\_step90\_120  
P5\_step120\_up  
P5\_nbouts\_sed  
P5\_alphasit  
P5\_parm1\_sit  
P5\_x50\_sit  
P5\_min\_t\_sit  
P5\_max\_t\_sit  
P5\_totsed  
P5\_nbouts\_sed\_tot  
P5\_ginisit  
P5\_mean\_period;

FORMAT Date date. waketime bedtime worktime offworktime datetime29.;  
DATALINES;

RUN;

\*Pull all filenames from directory;

filename DIRLIST pipe 'dir "X:\[name] Lab\Stand and Move  
ASU\_UMN\Data\ActivPAL\ISO\_TEST\SAS\_FILES>taggedfiles\T1\\*.csv" ';

## SMW Study Manual of Procedures

---

```
data dirlist ;
infile dirlist lrecl=200 trunccover;
input line $200.;
length file_name $ 130;
if input(substr(line,1,10), ?? mmddy10.) = . then delete;
file_name="X:\[name] Lab\Stand and Move
ASU_UMN\Data\ActivPAL\ISO_TEST\SAS_FILES>taggedfiles\T1"|| substr(line,40);
Mtime="1";
ID=substr(file_name,101,5);
ID2=Id*1;
Site=substr(id,1,3)*1;
keep file_name ID Mtime site ID2;
run;
```

\*Command to automatically create macro calls;

```
data test;
set dirlist end=end;
/*Where site>200;*/
/*where id2=10104;*/
count+1;

call symput ('filepath' || left(count), left(trim(file_name)));
call symputx ('ID' || left(count), ID);
call symputx ('Mtime' || left(count), Mtime);
if end then call symput('max', count);
run;
```

\*Write log directly to the specified text file to prevent interruptions;

```
proc printto log="X:\[name] Lab\Stand and Move
ASU_UMN\Data\ActivPAL\ISO_TEST\AP_Processing_04.23.18.log";
run;
```

```
%let datetime_start = %sysfunc(TIME()) ;
%put START TIME: %sysfunc(datetime(), datetime14.);
options mprint symbolgen;
```

```
%MACRO APimport(filepath, ID, Mtime);
%do i=1 %to &&max;
```

## SMW Study Manual of Procedures

---

```
*import AP event file;
DATA import;
    INFILE "&&filepath&i"
           LRECL=32760
    ENCODING="WLATIN1"
    TERMSTR=crlf
    DLM=','
    MISSOVER
           firstobs=2
    DSD ;
    INPUT Datetimevar
           Count
           Intervalold_s
           ActivityCode
           APCumulativeStepCount
           APActivityScoreMEThr
           validday_est
           Sleepbout
           ID
           Mtime
           ;
    boutid = _N_;
    sasdatetimenumber = (Datetimevar - 21916)*86400;*convert exceldate to
sasdatetime;
    CumulativeStepCount_i = APCumulativeStepCount;
    steps_n = APCumulativeStepCount - lag(CumulativeStepCount_i);
    if boutid = 1 then
        steps_n = APCumulativeStepCount;

    if Datetimevar in (0,.) then
        delete;          *remove rows of 0s from end of some activpal event files;
    if intervalold_s in (0,.) then delete;
    drop CumulativeStepCount_i;*non cumulative steps;
    if intervalold_s>=21600 then delete=1;else delete=0;

RUN;

*recalculate intervals as time between each bout -> more precise than the rounded data;
proc Sort data =import;
    by id descending boutid;
run;

data events (drop= Datetimevar intervalold_s APcumulativestepcount);
```

```
set import;
boutidR = _N_;
sasdatetimenumber_endbout = lag(sasdatetimenumber);

if sasdatetimenumber_endbout = . & sasdatetimenumber ne . then
    sasdatetimenumber_endbout = sasdatetimenumber + Intervalold_s;
Interval_s = sasdatetimenumber_endbout -
    sasdatetimenumber;
basicdate = datepart(sasdatetimenumber);
noondate = datepart(sasdatetimenumber + 43200);

*dates at beginning of bout
for day and for noon to noon window;
format sasdatetimenumber sasdatetimenumber_endbout datetime26.6 basicdate
noondate ddmmyy10.;
run;

proc Sort data =events;
    by id boutid;
run;

*Expand each event into 1-seconds epochs;

DATA events2; SET events;
If interval_s>=1 then interval_p=floor(interval_s);
    else if interval_s<1 then interval_p=interval_s;

do _i_ = 0 to Interval_s-(Interval_s/interval_p) by (Interval_s/interval_p); *preserves elapsed
time of non-whole number intervals;
    datetime3=sasdatetimenumber+_i_;
    output;
end;
format datetime3 datetime26.6 date date9.;
Run;

*recalualte interval between each epoch;

Proc sort data=events2;
by descending datetime3;
run;

data events2;set events2;
gap=lag(datetime3)-datetime3;
if gap>=1 then p=floor(gap);
```

## SMW Study Manual of Procedures

---

```
        else if gap<1 then p=gap;
date=datepart(datetime3);
if gap=. then delete;
```

```
run;
```

```
Proc sort data=events2;
by datetime3;
run;
```

```
*pull log data;
```

```
DATA windows3(drop=gap date noondate mtime); SET track.masterlogs2;
    WHERE ID=&&i&i*1;
    IF bedtime=. then delete;
```

```
        IF new_ootm=. then delete;
RUN;
```

```
*Merge logs with activpal data;
```

```
PROC SQL;
    CREATE TABLE APwake AS
    SELECT      t1.id,
                t1.Mtime,
                t1.Datetime3,
                t1.sasdatetimenumber,
                t1.sasdatetimenumber_endbout,
                t1.validday_est,
                t1.basicdate,
                t1.noondate,
                t1.activitycode,
                t1.Count,
                t1.gap,
                t1.Interval_s,
                t1.Steps_n,
                t1.boutid,
                t1.delete,
                t2.new_ootm,
                t2.bedtime,
                t2.MTS,
                t2.Sleeptime,
                t2.wake_freq,
                t2.total_time_awake,
```

```
t2.waketime,  
t2.ootm,  
t2.Workday,  
t2.MOT_to,  
t2.WorkTM,  
t2.OffWorkTM,  
t2.MOT_off,  
t2.Start,  
t2.End,  
t2.impute
```

```
FROM events2 AS t1  
NATURAL JOIN windows3 AS t2  
WHERE t1.datetime3 BETWEEN t2.new_ootm AND t2.Bedtime  
ORDER BY t1.ID, t1.datetime3;
```

```
QUIT;
```

```
RUN;
```

\* export dataset to create intermediate files that can be re-analyzed for later use;

```
Data "X:\[name] Lab\Stand and Move  
ASU_UMN\Data\ActivPAL\ISO_TEST\SAS_FILES\DATASETS\MetaData\APWake_&&i.._T  
&&Mtime&i"; set ApWake;  
Run;
```

\*Calculate cadence;

```
data step; set APwake;
```

```
Activity_code2 = Activitycode;
```

\*calculating a 0/1 variable for whether the event is stepping (and relevant, to be included) or not;  
ActStep =0;

```
if Activity_code2 =2 then ActStep = 1;
```

```
if ActStep = 1 then newstepbout = 1;
```

\*calculating a 0/1 variable for whether the relevant stepping event is part of a new stepping bout  
or not;

```
if ActStep = 1 & ActStep = lag(ActStep) then newstepbout = 0;
```

```
newbout = 0;
```

```
if Activity_code2 in (.,0,1) then newbout = 1;
```

```
if Activity_code2 =2 & newstepbout=1 then newbout = 1;
```

## SMW Study Manual of Procedures

---

```
If delete=1 then delete;* remove potential non-wear: bouts>6 hrs;
run;
```

```
data step2;
set step;
by id;
*numbering the stepping bouts [newboutid];
if first.id then newboutid = 0;
if newbout = 1 then newboutid + 1;
run;
```

```
proc means data = step2 noprint;
by id newboutid;
where ActStep = 1;
output out=step3 min(sasdatetimenumber)=bs_dt max(sasdatetimenumber_endbout)=be_dt
sum(steps_n)=steps_n;
;
run;
```

```
data step3 (keep= ID newboutid cadence stepboutdur);
set step3;
*date the stepping bout began for later aggregation;
```

```
basicdate = datepart (bs_dt);
*duration of the stepping bout;
stepboutdur = be_dt - bs_dt;
```

```
*cadence;
cadence = 2*steps_n/(stepboutdur/60);
```

```
run;
```

```
Proc SQL;
    Create table cadence as
        select a.*,
               b.Cadence,
               b.stepboutdur
    From step2 as a
    Left join step3 as b
    on a.ID=b.ID and a.newboutid=b.newboutid
    order by a.Datetime3;
Quit;
```

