## SMW Study Manual of Procedures

---

\*categorize epochs into either SED STAND LPA MVPA;

Data cadence2(drop=sasdatetimenumber);set cadence;  
if start<=datetime3<=end then delete; \*Delete errors/non-wear time;

date=datepart(datetime3);

IF Workday=2 or WorkDay=0 THEN Status=1; /\*nonworkday\*/  
IF Workday=1 AND WorkTM <= datetime3 <= OffWorkTM THEN Status=2; /\*atwork\*/  
IF Workday=1 AND not (WorkTM <= datetime3 <= OffWorkTM) THEN  
Status=3; /\*offwork\*/  
  
IF activitycode=2 AND cadence ge 100 THEN act\_intensity=3; /\*MVPA\*/  
ELSE IF activitycode=2 AND cadence lt 100 then act\_intensity=2; /\*LPA\*/  
ELSE IF activitycode=1 THEN act\_intensity=1; /\*Standing\*/  
ELSE IF activitycode=0 THEN act\_intensity=0; /\*Sitting\*/

%MACRO PERIOD(tt); \*Defines macro with variable (I chose to call it tt for time) that will be set  
to 1-5;

%If &tt.=1 %then %do;

%Let P=1;

%end;

%If &tt.=2 %then %do;

%Let P=2;

%end;

%If &tt.=3 %then %do;

%Let P=3;

%end;

%If &tt.=4 %then %do;

%Let P=2 3;

%end;

%If &tt.=5 %then %do;

%Let P=1 2 3;

%end;

IF status in (&P.) then P&TT.=gap; else P&TT.=0;

IF status in (&P.) and act\_intensity=0 then P&TT.\_Sit=gap;  
else P&TT.\_Sit=0;

IF status in (&P.) and act\_intensity ge 1 and lag(act\_intensity)=0 then P&TT.\_Sitstand=1;  
else P&TT.\_SitStand=0;

IF status in (&P.) and act\_intensity=0 and interval\_s>=1800 then  
P&TT.\_long\_sitbout\_ct=1/floor(interval\_s);  
else P&TT.\_long\_sitbout\_ct=0;

IF status in (&P.) and act\_intensity=0 and interval\_s<1800 then  
P&TT.\_short\_sitbout\_ct=1/floor(interval\_s);

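### The printed activPAL code miscomputes the cadence that separates LPA from MVPA: it counts steps once per expanded row and drops events shorter than 1 s

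*Combined protocol and SAP*

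**What the plan says.** Section 10.3 names sitting time and LPA at work as the primary outcomes, and H1 concerns LPA. The header of the SAS code in Appendix 1.4 defines LPA as "Total minutes spent on LPA (stepping activities with cadence <100 steps/mins". The classification step applies that cut-point: "ELSE IF activitycode=2 AND cadence lt 100 then" the row is LPA, and stepping rows at 100 or more are MVPA.

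The cadence is built in four steps.

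- Event times are converted from Excel serial dates by "sasdatetimenumber = (Datetimevar - 21916)*86400;*convert exceldate to" SAS datetimes, and event lengths are recomputed as differences between successive times. `steps_n` is set once per event, as the change in the cumulative count.
- Each event is expanded into rows of about one second by "do _i_ = 0 to Interval_s-(Interval_s/interval_p) by (Interval_s/interval_p"), with the output statement inside the loop. The divisor `interval_p` is the floor of the interval when that is at least 1 s. Below 1 s the rule is "else if interval_s<1 then interval_p=interval_s".
- The row-level table is summarised by stepping bout. Steps are totalled as "sum(steps_n)=steps_n"; duration is the latest event end minus the earliest event start.
- Cadence is then "cadence = 2*steps_n/(stepboutdur/60").

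**The concern.** The numerator and denominator of the cadence are on different footings. Every row of an event carries that event's full step count, so the row sum counts the steps as many times as there are rows. The duration is counted once. Nothing between the expansion and the cadence formula divides by the number of rows or keeps one row per event. The same program does correct for row copying elsewhere: sitting-bout counts are weighted by "ct=1/floor(interval" in seconds). Steps receive no such weight.

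The second problem lies in the sub-second branch, where the loop's upper limit is negative and no row is written.

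This cadence alone decides whether stepping time counts as LPA. The first error moves some slow stepping out of LPA; the second moves some brisk walking into LPA or standing. Both arms pass through the same code, but Section 7.1 gives them different targets (STAND+ adds standing for half of desk time). The mix of short slow steps and brisk walks may therefore differ by arm, and cancellation cannot be assumed. Sitting time (H2) is essentially unaffected.

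**Working it through.** The plan states no figure to reproduce, so the check follows the printed logic and puts numbers through it. The inputs are the code lines above. The factor 2 in the cadence formula implies that one count is one stride. The examples assume one stride per event unless stated, because the documents do not say what a row holds.

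**Rows per event.** Let T be the computed interval.
- T ≥ 1 s: increment = T/floor(T), upper limit = T − T/floor(T), so floor(T) rows are intended. Because the loop index is non-integer, rounding sometimes drops the last row. On a 0.1 s grid from 1 to 60 s, 206 of 591 exact durations give floor(T) − 1 rows and the rest give floor(T).
- T < 1 s: increment = T/T = 1, upper limit = T − 1 < 0, so no row is written.

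**Error 1, inflation.** For one stride of T seconds, true cadence = 120/T and coded cadence = 120 × rows/T.
- Ten strides of 2.2 s: true 2 × 10/(22/60) = 54.5. Two rows each give 2 × 20/(22/60) = 109.1, coded MVPA.
- Isolated strides of 2.1–2.3, 4.1–4.7 and 5.1–5.9 s (true 52–57, 26–29 and 20–24) are coded MVPA under every timestamp format tested. Strides of 2.5–2.9, 3.7–3.9 and 4.9 s stay LPA with inflated cadence. Others, such as 2.0, 2.4 and 3.0–3.6 s, fall either way by format.
- Slow walks of 20 strides with mean 2.0–3.5 s and an assumed SD of 0.5 s (true cadence 34–60) are coded 90–98 on average and stay LPA in 72–99% of simulated runs. With mean 2.2 s and SD 0.05 s, all become MVPA.
- If a row holds several strides, the inflation is larger. Five strides in a 10 s row have true cadence 2 × 5/(10/60) = 60. With 8 to 10 rows the coded cadence is 480 to 600.

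**Error 2, loss.**
- Twenty strides alternating 1.1 and 0.9 s: true 2 × 20/(20/60) = 120. Only the ten 1.1 s strides produce rows, and the bout ends at 19.1 s, so coded cadence = 2 × 10/(19.1/60) = 63, LPA.
- Twenty strides of 0.9 s after standing: true 2 × 20/(18/60) = 133. No stepping row exists, and the 18 s are added to standing.
- Nominal 1.0 s strides depend on how timestamps are stored. With event times on a 0.1 s grid, each rounded separately to an Excel serial date, the share computing below 1 s is 37% at full double precision, 26% at 10 decimals and 59% at 8 decimals. Twenty equal 1.0 s strides (true 120) are then coded 78, 91 and 53 on average, and in all 500 runs at each precision they are coded LPA or standing. With exact times they are coded 120.

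**Where the code is right.** Events of 1.1–1.9 s give exactly one row, and equal strides of that length are classified correctly.

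**The case against.** The strongest reply is that the listing may not be the analysis program. It reads only T1, from a test folder, writes a log dated 04.23.18, and contains strings that could not run as printed, some of which may be PDF misreads. Its input files already carry derived fields, so an earlier, unseen step fixed what one row contains. This stands: the defect is certain for the printed code and unverified for production.

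A second reply is size. Equal strides from 1.1 to 1.9 s, which bracket the cut-point at 1.2 s, are handled correctly, and most irregular slow walks stay LPA. Section 12.2 gives a detectable LPA difference of 12.2 min per 8-hour day, or 732 s. Reaching it would need a net between-arm excess of about 732/2.2 = 333 misclassified isolated 2.2 s strides per day, or 732/20 ≈ 37 misclassified 20 s brisk bouts. This is a fair reason not to presume a large bias in the contrast. It does not show that the bias is small, since stride lengths, row content and timestamp precision are all unstated and multi-stride rows would be affected far more.

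A third reply is that both arms share the code. That makes the rule common to both arms; it does not make the mix of stepping common, so a differential effect is possible but not shown.

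The loop's comment about keeping elapsed time for fractional intervals does not help, because it concerns time and not steps.

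**Conclusion.** The concern holds for the code as printed. Cadence for events of about 2 s or more is multiplied by the number of rows written (floor of the interval, or one fewer), and events computing below 1 s are lost. Individual bouts can be wrong by a factor of about two in either direction (54.5 coded 109.1; 120 coded 63), and by more if rows hold several strides. These examples rest on assumed stride lengths and, for 1.0 s strides, on assumed timestamp storage. The net effect on work-time LPA and on the H1 contrast is unknown in sign and size. The derivation should be corrected before LPA, MVPA or standing is analysed. It becomes more pressing if the production code for T1–T4 is found to match.

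**What to change.** 1. Establish whether the production code for T1 to T4 contains this logic.
2. Run the printed and corrected code on a few stored event files and report the change in `P2_LPA`, `P2_MVPA` and `P2_Stand`. This supplies the sign and size that the documents cannot. Include `P2_step_ct`, which adds one per row and so also depends on row count.
3. If confirmed, compute bout steps, duration and cadence on the event-level table (one record per `boutid`) before expansion, and merge cadence back by `boutid`, which the later table already carries.
4. In the expansion, write exactly one row at the event start when the interval is below 1 s. Otherwise loop on an integer index from 0 to floor(interval) − 1.
5. Guard the short sitting-bout count, whose divisor would be zero for any sub-second sitting row once such rows exist. SAS would set that row's count to missing and the sum would skip it.
6. Rerun all time points before any LPA, MVPA or standing analysis.

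In the check, code corrected in this way misclassified 0 of 5,475 test walks and single strides (20 walks exactly at the cut-point were set aside). The cost is a few lines of SAS and a rerun on stored files, with no new data.

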## SMW Study Manual of Procedures

---

\*categorize epochs into either SED STAND LPA MVPA;

Data cadence2(drop=sasdatetimenumber);set cadence;  
if start<=datetime3<=end then delete; \*Delete errors/non-wear time;

date=datepart(datetime3);

IF Workday=2 or WorkDay=0 THEN Status=1; /\*nonworkday\*/  
IF Workday=1 AND WorkTM <= datetime3 <= OffWorkTM THEN Status=2; /\*atwork\*/  
IF Workday=1 AND not (WorkTM <= datetime3 <= OffWorkTM) THEN  
Status=3; /\*offwork\*/  
  
IF activitycode=2 AND cadence ge 100 THEN act\_intensity=3; /\*MVPA\*/  
ELSE IF activitycode=2 AND cadence lt 100 then act\_intensity=2; /\*LPA\*/  
ELSE IF activitycode=1 THEN act\_intensity=1; /\*Standing\*/  
ELSE IF activitycode=0 THEN act\_intensity=0; /\*Sitting\*/

%MACRO PERIOD(tt); \*Defines macro with variable (I chose to call it tt for time) that will be set  
to 1-5;

%If &tt.=1 %then %do;

%Let P=1;

%end;

%If &tt.=2 %then %do;

%Let P=2;

%end;

%If &tt.=3 %then %do;

%Let P=3;

%end;

%If &tt.=4 %then %do;

%Let P=2 3;

%end;

%If &tt.=5 %then %do;

%Let P=1 2 3;

%end;

IF status in (&P.) then P&TT.=gap; else P&TT.=0;

IF status in (&P.) and act\_intensity=0 then P&TT.\_Sit=gap;  
else P&TT.\_Sit=0;

IF status in (&P.) and act\_intensity ge 1 and lag(act\_intensity)=0 then P&TT.\_Sitstand=1;  
else P&TT.\_SitStand=0;

IF status in (&P.) and act\_intensity=0 and interval\_s>=1800 then  
P&TT.\_long\_sitbout\_ct=1/floor(interval\_s);  
else P&TT.\_long\_sitbout\_ct=0;

IF status in (&P.) and act\_intensity=0 and interval\_s<1800 then  
P&TT.\_short\_sitbout\_ct=1/floor(interval\_s);

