### 10.3 ActivPAL

Our primary outcomes, time spent sitting and LPA at work, will be assessed with the activPAL3 micro accelerometer (PAL Technologies, Glasgow, United Kingdom) for seven consecutive days at each measurement time point. The activPAL will be waterproofed using medical grade adhesive covering and attached to the midline of the thigh using a breathable, hypoallergenic tape. This method allows for the monitor to be worn continuously for seven consecutive days without removing for bathing or other water-based activities (a valuable feature that reduces missing data). Additional adhesive dressing will be given to all participants for re-application as necessary. The primary outputs of the activPAL are time spent sitting, time spent upright, and time spent "stepping." Participants concurrently will complete an online daily log where they will report their sleep/wake schedule and time arriving and departing their workplace. The daily logs will be used to filter time spent sitting and LPA during work hours. In addition, any uninterrupted sedentary bouts of more than 6 h that occur within reported wake times will be considered non-wear times and treated as missing data. Days with  $<10$  h of monitor wear data or  $<4$  hours of reported work time as monitor wear data will be excluded from analyses. Outcomes will be reported as a standardized 8 h workday to account for differences in total work time. Full details of activPAL initialization, wear, and download protocol are in Appendix 1.

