## SMW Study Manual of Procedures

---

```
        else P&TT._short_sitbout_ct=0;
IF status in (&P.) and act_intensity=0 and interval_s>=1800 then P&TT._long_sitbout_dur=gap;
        else P&TT._long_sitbout_dur=0;
IF status in (&P.) and act_intensity=0 and interval_s<1800 then P&TT._short_sitbout_dur=gap;
        else P&TT._short_sitbout_dur=0;
IF status in (&P.) and act_intensity=1 then P&TT._Stand=gap;
        else P&TT._Stand=0;
IF status in (&P.) and act_intensity=2 then P&TT._LPA=gap;
        else P&TT._LPA=0;
IF status in (&P.) and act_intensity=3 then P&TT._MVPA=gap;
        else P&TT._MVPA=0;
IF status in (&P.) and activitycode=2 then P&tt._step_min=gap;
        else P&tt._step_min=0;
IF status in (&P.) and activitycode=2 then P&tt._step_ct=1;
        else P&tt._step_ct=0;
IF status in (&P.) and activitycode=2 then DO;
        if stepboutdur<5 then P&tt._step00_05=gap;
            else P&tt._step00_05=0;
        if 5<=stepboutdur<10 then P&tt._step05_10=gap;
            else P&tt._step05_10=0;
        if 10<=stepboutdur<15 then P&tt._step10_15=gap;
            else P&tt._step10_15=0;
        if 15<=stepboutdur<30 then P&tt._step15_30=gap;
            else P&tt._step15_30=0;
        if 30<=stepboutdur<60 then P&tt._step30_60=gap;
            else P&tt._step30_60=0;
        if 60<=stepboutdur<90 then P&tt._step60_90=gap;
            else P&tt._step60_90=0;
        if 90<=stepboutdur<120 then P&tt._step90_120=gap;
            else P&tt._step90_120=0;
        if stepboutdur>=120 then P&tt._step120_up=gap;
            else P&tt._step120_up=0;
        End;
```

%MEND; \*Ends macro;

%PERIOD(1); \*Runs for P1 variables;

%PERIOD(2); \*Runs for P2 variables;

%PERIOD(3);

%PERIOD(4);

%PERIOD(5);

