## SMW Study Manual of Procedures

---

```
%let dir = X:\[name] Lab\Stand and Move
ASU_UMN\Data\ActivPAL\ISO_TEST\SAS_FILES>taggedfiles\T1;
%APimport;

proc printto;
run;

%put END TIME: %sysfunc(datetime(),datetime14.);
%put PROCESSING TIME:
%sysfunc(putn(%sysvalf(%sysfunc(TIME())-&datetime_start.),mmss.)) (mm:ss) ;

Proc SQL;
Create table Activpal as
select a.*,
       b.workday
From iso.Report_Final as a
Left join track.masterlogs2 as b
ON a.ID=b.ID and a.date=b.date
Order by a.ID, a.date;
Quit;

Data iso.AP_Final;
set Activpal;

if workday=0 and p1_min<600 then valid_p1=0;
if workday=0 and p1_min>=600 then valid_p1=1;
if workday=1 and p2_min<240 then valid_p2=0;
if workday=1 and p2_min>=240 then valid_p2=1;
if workday=1 and p3_min<240 then valid_p3=0;
if workday=1 and p3_min>=240 then valid_p3=1;

run;
```

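### A workday log with a missing arrival or departure time is misclassified by the SAS work-hours test and can still pass a validity flag; whether such logs reach that step is not shown, and the trial-level effect is probably small

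*Combined protocol and SAP*

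**What the plan says.** Section 10.3 states the purpose of the logs: "The daily logs will be used to filter time spent sitting and LPA during work hours". It also excludes days with under 4 h of worn, reported work time, and rescales the outcomes to an 8 h workday.

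The SAS code in Appendix 1.4 carries this out in five steps.

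- **Log records dropped.** There are two checks: "IF bedtime=. then delete" and "IF new_ootm=. then delete". Neither work time is checked.
- **Waking window.** The join keeps epochs that satisfy "WHERE t1.datetime3 BETWEEN t2.new_ootm AND t2.Bedtime".
- **Work window.** At-work status comes from "IF Workday=1 AND WorkTM <= datetime3 <= OffWorkTM THEN Status=2". The off-work branch (Status 3) is its exact complement: "IF Workday=1 AND not (WorkTM <= datetime3 <= OffWorkTM) THEN". Both tests recur in the data step that feeds the bout-pattern variables.
- **Outcomes.** LPA is accumulated by "IF status in (&P.) and act_intensity=2 then P&TT._LPA=gap", and sitting in the same way. Set P2 is Status 2, P3 is Status 3, P4 is Status 2 and 3, and P5 is all three.
- **Validity.** The work-time flag is "if workday=1 and p2_min>=240 then valid_p2=1". Off-work time has a parallel flag, `valid_p3`, with the same 240-minute threshold. P4 and P5 have none.

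A variable `impute` is carried over from the log file `masterlogs2`, but the printed code never uses it and the documents never define it. No rule is given for a workday log with one work time missing.

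**The concern.** In a SAS comparison a missing value is smaller than any number. With arrival missing, the lower half of the work-window test is always true, so the window opens at the start of the waking day. With departure missing, the upper half is always false, so no epoch counts as work and all of them count as off-work.

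The first case affects the primary outcomes. Time at home and commuting is counted as work, which section 10.3 does not allow. Rescaling to 8 h does not remove the error, because the mix of activity changes and not only the total. The validity flag uses the same inflated minutes, so it becomes easier to pass. The second case leaves the primary outcomes alone but corrupts the off-work variables.

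The checks on bedtime and `new_ootm` suggest that missing log times were expected at this step. The work window has no equivalent check.

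**Working it through.** The plan has no figure of its own to reproduce here. The check traces the code and then sizes the effect under assumptions.

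**1. Logic.** Assumed day: up 06:00, bed 22:00 (960 waking minutes). Minutes are rounded.

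| Log | P2 (work) | P3 (off-work) | `valid_p2` | `valid_p3` |
|---|---|---|---|---|
| Complete, 08:00-17:00 | 540 | 420 | 1 | 1 |
| Arrival missing, leaves 17:00 | 660 | 300 | 1 | 1 |
| Departure missing | 0 | 960 | 0 | 1 |
| Both missing | 0 | 960 | 0 | 1 |
| Complete, 09:00-12:00 | 180 | 780 | 0 | 1 |
| Arrival missing, leaves 12:00 | 360 | 600 | 1 | 1 |

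Row 2 adds 120 min of non-work time (120/540 = 22%). Rows 5 and 6 show a day that fails the 4 h rule with a complete log and passes it once the arrival time is lost.

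**2. Size on one affected day.** Assumed inputs: 540 min at work; *h* = 60-180 min between getting up and arriving; sitting share *p* = 0.65-0.75 at work and *q* = 0.30-0.70 before work.

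Shift in sitting per 8 h = (*q* - *p*) × *h*/(540 + *h*) × 480

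- Lowest: (0.30 - 0.75) × 180/720 × 480 = -54.0 min
- Middle: (0.50 - 0.75) × 120/660 × 480 = -21.8 min
- Highest: (0.70 - 0.65) × 180/720 × 480 = +6.0 min

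The same formula for LPA, assuming 6-8% of time at work and 10-20% before work:

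- Smallest: (0.10 - 0.06) × 60/600 × 480 = +1.9 min
- Largest: (0.20 - 0.06) × 180/720 × 480 = +16.8 min

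If the arms do not differ before work, the arm difference on that day is diluted by *h*/(540 + *h*): 60/600 = 10%, 120/660 = 18.2%, 180/720 = 25%.

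**3. Size across the trial.** The share *f* of affected days is not in the documents. For the middle case, with days weighted equally:

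| *f* | Mean sitting shift (*f* × 21.8) | Dilution (*f* × 18.2%) |
|---|---|---|
| 1% | -0.22 min | 0.18% |
| 5% | -1.09 min | 0.91% |
| 10% | -2.18 min | 1.82% |

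The most extreme inputs at *f* = 10% give 0.10 × 54 = 5.4 min and 0.10 × 25% = 2.5%.

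A mean shift that is equal in both arms cancels in the contrast and leaves only the dilution. At 1.82%, a true difference of 14.6 min would lose 0.0182 × 14.6 = 0.27 min. If the share differed between arms, the bias in the middle case would be that difference × 21.8 min, so 5 percentage points would give about 1.1 min.

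**The case against.** The strongest reply is that the fault may never occur. It needs a `masterlogs2` row coded as a workday with one work time missing. That file is already processed: it holds both `ootm` and `new_ootm`, a workday code, error windows and `impute`. Work times may have been completed upstream, or the workday code may require both. The documents do not show this either way, so the point must stay conditional. A reader might infer that the primary outcomes are contaminated; the documents support only that they would be if such rows exist.

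A reader might also set the shift on one day beside the 14.6 min detectable difference in section 12.2. That comparison does not hold. The 14.6 min is a between-arm difference in means, whereas the shift is a change in level on a single day. Outcomes draw on up to seven days of wear, and equal shifts cancel.

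The direction is not fixed either. Commuting may be seated, and the assumed range includes a small positive shift in sitting. The dilution figure also needs care: section 7.3 gives the arms different goals and messages as well as different desks, so equality of the arms before work is an assumption.

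Section 11.4 promises a check for improbable values, and work minutes are output by day. An inflated window might be noticed, but an 11-hour work window need not look improbable. Finally, the printed code reads only T1 files from a test folder; its reuse at 12 months is plausible but not shown.

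These points limit the size and certainty of the effect. They do not change how the printed code would handle such a row.

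**Conclusion.** The point holds in conditional form. If a workday log reaches this code with a departure time and no arrival time, at-work sitting and LPA include time before work, and the day can be kept contrary to section 10.3. A missing departure time is not harmless, as a reader might infer from `valid_p2` being 0. The whole waking workday is then counted as off-work time and passes `valid_p3`.

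The code behaviour is certain. The number of affected days is unknown, and every magnitude above rests on assumed clock times and activity shares. With 1-10% of days affected and mid-range inputs, the effect across the trial is probably small unless missing arrival times are more common in one arm. The case for acting is that a wrong primary-outcome value on such days is cheap to prevent and easy to count.

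**What to change.** 1. In both places where Status is assigned, test the work times first. When `Workday=1` and `WorkTM` or `OffWorkTM` is missing, or `OffWorkTM` is not later than `WorkTM`, assign a separate code such as Status 4.
2. Leave Status 4 out of sets P2 and P3, and add it to P4 and P5 in both macros that define the sets. Leaving Status unassigned would be worse: P4 and P5 would become false zeros, with no validity flag to reveal them.
3. Set `valid_p2` and `valid_p3` to 0 for these days. Zero minutes already produces this, but it should be explicit.
4. State the rule for incomplete work times in section 10.3, and define `impute` and `new_ootm`.
5. Report the number of such days by arm and visit. A count of zero at every visit would settle the matter.

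The cost is a few lines of code and a rerun. Days with complete, correctly ordered work times are unchanged. The downside is that a few workdays with incomplete logs drop out of the work and off-work outcomes.
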